# Further details are included in the Pharmacy Manual.

The trial pharmacy team will dispense sufficient trial drug for 6 months' supply at visit 1 (week 0) and visit 4 (week 25).

The participant will stop taking trial drug on the day of their research surveillance colonoscopy (visit 5; approximately week 52).

If a participant misses a dose on one day, they should resume taking their normal daily dose the next day. If the participant vomits straight after dosing they will be advised not to take an additional dose to make up for it. If the investigator feels that the reason for inadequate adherence is temporary, the participant will be advised to resume taking their trial drug. The participant will stop taking trial drug on the day of their exit surveillance colonoscopy.

# 9.7 Dosage modifications

Dose reduction for the sub-trial is not permitted. If participants experience GI symptoms, they will be advised to take their full dose with or after food. If symptoms persist, participants can divide their dose such that two capsules are taken each morning and two in the evening. In this situation the participant must take the capsules from the same 2 bottles each morning and evening to allow for the dose blinding. In order to assist with this, each bottle within a treatment pack will be easily distinguished (e.g. numbers 1-4/different colours/letters A-D) from one another.

#### 9.8 Known drug reactions and interaction with other therapies

The most common side effects of resveratrol are gastrointestinal in nature, comprising diarrhoea, constipation, nausea, abdominal cramps, vomiting, steatorrhoea, heartburn, reflux and bloating.

For the full list of undesirable effects are detailed in the regulatory approved Investigators Brochure (IB) for resveratrol provided in the Investigator and Pharmacy Site Files (ISF).

#### 9.9 Concomitant medication

There is evidence from two *in vivo* studies in preclinical models suggesting that taking resveratrol in combination with the **anti-clotting agent warfarin** increases the risk of bleeding, therefore patients taking warfarin would be ineligible for COLO-PREVENT.

IRAS: 1005142 Page **69** of **109** 

#### Permitted medications

The guidance for permitted medications is as per the main trial; see section 8.9.

# Not-permitted medication

Medications not permitted include warfarin

#### Medications to be used with caution

Based on pharmacokinetic studies, resveratrol may theoretically interfere with phase I metabolism of certain drugs due to its inhibitory effects on cytochrome P450. In theory, drugs relying on first pass metabolism for activation/efficacy (such as some statins, antifungals and anti-histamines) may be rendered less effective during co-administration of resveratrol. All concomitant medication should be carefully reviewed by the clinical team prior to trial enrolment to ensure that participant safety is maintained, and efficacy of concomitant medication is not compromised.

If a contraindicated medication is required for treatment of a clinical event while the participant is on study they should be withdrawn from trial treatment and permission requested to continue to collect data.

#### 9.10 Trial restrictions

Eligibility criteria have been formulated so that individuals with an increased risk of serious toxicity are excluded. Details of any concomitant illness (any illness present at the start of the trial) should be recorded at trial entry. If a change influences the participant's eligibility to continue in the trial, the investigator must be informed.

Trial participants must abstain from ingestion of OTC supplements containing resveratrol for the trial duration.

There are no special dietary requirements or restrictions for the sub-trial. Following consultation with PPI representatives, it is not believed to be practical to attempt to restrict dietary consumption of foods/drinks containing resveratrol as this could adversely affect recruitment, compliance and retention. The sub-trial is designed to be pragmatic and applicable to a real world setting.

Male participants and their female partners of child bearing potential must use medically acceptable forms of contraception during the trial. See section 8.10 on definitions of WOCBA and adequate contraception; definition on pregnancy reporting process is described in section 10.5.

# 9.11 Assessment and compliance with treatment

# Adherence

A high rate of adherence to treatment is required and Investigators are responsible for ensuring that participants understand this. Prior to registration, Investigators and any other trial staff involved in the consent process should ensure that participants fully understand the trial treatment and the importance of adherence, and this should be re-iterated at face-

IRAS: 1005142 Page **70** of **109** 

Page **71** of **109** 

to-face (or telephone) follow-up visits at the specified time points and adherence should be positively encouraged. Patient-reported adherence should be recorded on follow-up CRFs.

Compliance with trial drug will be assessed by pill counting (returns of unused medication). Returns of residual pills will be recorded in accountability logs retained in pharmacy and the electronic Case Report Form (eCRF).

- If treatment ceased for 6 or less days no action taken.
- If ≥7 days record on the CRF.
- If treatment is paused and >20% of doses are missed for any reason, it is at the discretion of site investigators as to whether it is appropriate to restart trial treatment.
- All treatment pauses must be recorded in the CRF.

# 9.12 Name and description of each Non-Investigational Medicinal Product (NIMP)

The two doses of resveratrol will be compared to placebo in the sub-trial. The placebo will be manufactured to match the 5mg and 250 mg resveratrol capsules, and will contain no active ingredients.

# 10. ADVERSE EVENT MANAGEMENT / PHARMACOVIGILANCE

#### 10.1 Definitions

Term	Definition
Adverse Event (AE)	Any untoward medical occurrence in a participant to whom a medicinal product has been administered, including occurrences which are not necessarily caused by or related to that product.
Adverse Reaction (AR)	An untoward and unintended response in a participant to an investigational medicinal product which is related to any dose administered to that participant.
	The phrase "response to an investigational medicinal product" means that a causal relationship between a trial medication and an AE is at least a reasonable possibility, i.e. the relationship cannot be ruled out.
	All cases judged by either the reporting medically qualified professional or the Sponsor as having a reasonable suspected causal relationship to the trial medication qualify as adverse reactions. It is important to note that this is entirely separate to the known side effects listed in the SmPC. It is specifically a temporal relationship between taking the drug, the half-life, and the time of the event or any valid alternative etiology that would explain the event.
Serious Adverse Event (SAE)	A serious adverse event is any untoward medical occurrence that:

IRAS: 1005142

	 
	
 
results in death
 
is life-threatening
 
requires inpatient hospitalisation or prolongation of existing hospitalisation
 
results in persistent or significant disability/incapacity
 
consists of a congenital anomaly or birth defect
 
Other 'important medical events' may also be considered serious if they jeopardise the participant or require an intervention to prevent one of the above consequences.
 

	NOTE: The term "life-threatening" in the definition of "serious" refers to an event in which the participant was at risk of death at the time of the event; it does not refer to an event which hypothetically might have caused death if it were more severe.
Serious Adverse Reaction (SAR)	An adverse event that is both serious and, in the opinion of the reporting Investigator, believed with reasonable probability to be due to one of the trial treatments, based on the information provided.
Suspected Unexpected Serious Adverse Reaction	A serious adverse reaction, the nature and severity of which is not consistent with the information about the medicinal product in question set out in the reference safety information:
(SUSAR)	
 
in the case of a product with a marketing authorisation, this could be in the summary of product characteristics (SmPC) for that product, so long as it is being used within its licence. If it is being used off label an assessment of the SmPCs suitability will need to be undertaken.
 

	
 
in the case of any other investigational medicinal product, in the Investigator's Brochure (IB) relating to the trial in question
 

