## 10.2 Recording and reporting SAEs, SARs AND SUSARs

All SAEs, except those defined as exempt above, and SUSARs occurring from first administration of trial drug up to the routine visit post-surveillance colonoscopy (visit 10 for the main trial; and visit 6 for the resveratrol sub-trial) or 14 days post cessation of trial treatment where this occurs earlier than protocolised, are subject to expedited reporting. This should be conducted in accordance with the Sponsor SOP for reporting SAEs and on the COLO-PREVENT SAE Report Form. Completed forms should be emailed to the Sponsor ([contact]) and Leicester CTU ([contact]) immediately and within 24 hours of the research staff becoming aware of the event. All SAEs will be reviewed and tracked by the Sponsor (or their delegate) until resolution. Monthly line listings of all SAEs are reviewed by the Director of Research and Development on a monthly basis. Please note: the 14 day safety monitoring period following last dose is greater than 5X half-lives of all trial drugs.

For each **SAEs / SUSARs** the following information will be collected:

- full details in medical terms and case description
- event duration (start and end dates, if applicable)
- action taken
- outcome
- seriousness criteria
- causality (i.e. relatedness to trial drug / investigation), in the opinion of the investigator
- whether the event would be considered expected or unexpected.

Any change of condition or other follow up information should be emailed to Sponsor and Leicester CTU as soon as it is available or at least within 24 hours of the information becoming available. Events will be followed up until the event has resolved or a final outcome has been reached.

IRAS: 1005142 Page **73** of **109** 

The causality and expectedness of the SAE should be assessed by the Investigator(s) or another delegated medic on the SAE form.

For participants on the main trial, section 4.8 of the SmPC for aspirin and metformin will be used to assess expectedness of events (known as the reference safety information).

For participants on the resveratrol sub-trial, section 8.0 of the IB for resveratrol will be used to assess expectedness of events (known as the reference safety information).

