Any SAE assigned by the Investigator or delegate as being related to the allocated treatment and unexpected according to the approved reference safety information will be classified as a "SUSAR" and is subject to expedited reporting to the Competent Authority (the MHRA) and the REC. The Sponsor or delegate will liaise with the Principal Investigator and Chief Investigator to ensure that the relevant eSUSAR report is completed and submitted to the Competent Authority (the MHRA) within the required timeframes. The Sponsor will then submit the eSUSAR report and safety report to the REC. Fatal or life-threatening SUSARs must be reported within 7 days and all other SUSARs within 15 days. Follow up reports must be provided in a timely manner and as per the request of the Sponsor or delegate.

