## Chief Investigator (CI) / delegate or independent clinical reviewer:

- 1. Clinical oversight of the safety of patients participating in the trial, including an ongoing review of the risk / benefit.
- 2. Using medical judgement in assigning seriousness, causality and expectedness of SAEs where it has not been possible to obtain local medical assessment.
- 3. Immediate review of all SUSARs.
- 4. Review of specific SAEs and SARs in accordance with the trial risk assessment and protocol.
- 5. Preparing the clinical sections and final sign off of the Development Safety Update Report (DSUR).

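### Section 10 defines an adverse reaction and a serious adverse reaction by different causality tests and assessors, leaving an unexpected SAE suspected only centrally with no stated route to expedited reporting

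*Protocol*

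**What the plan says.** The definitions table in Section 10.1 sets the causality test for an adverse reaction (AR) at its lowest level: "a causal relationship between a trial medication and an AE is at least a reasonable possibility, i.e. the relationship cannot be ruled out". It names two possible assessors: "All cases judged by either the reporting medically qualified professional or the Sponsor as having a reasonable suspected causal relationship to the trial medication qualify". Nothing in that row limits it to non-serious events.

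The SAR row starts again from the term adverse event. It asks that the event be serious and, "in the opinion of the reporting Investigator, believed with reasonable probability to be due to one of the trial treatments".

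The SUSAR row begins: "A serious adverse reaction, the nature and severity of which is not consistent with the information about the medicinal product in question".

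Section 10.2 says how this is applied. The SAE form records "causality (i.e. relatedness to trial drug / investigation), in the opinion of the investigator". The rule for SUSAR status and onward reporting to the MHRA and REC covers "Any SAE assigned by the Investigator or delegate as being related to the allocated treatment and unexpected according to the approved reference safety information".

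Section 10.3 has the principal investigator assign causality. It has the CI, a delegate or an independent reviewer assign "causality and expectedness of SAEs where it has not been possible to obtain local medical assessment". The Sponsor's listed duties are to collect and verify safety data, pass it to the CI and the oversight committees, and forward SUSARs. Judging or raising causality is not among them.

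**The concern.** Two things change between the AR and SAR rows. The threshold moves from a possibility that cannot be excluded to a reasonable probability, and the Sponsor drops out as an assessor. The SAR row does not refer back to the AR row, so it does not inherit the AR test.

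Expedited reporting to the MHRA and REC, notification of other investigators, and any tabulation of SARs and SUSARs all depend on the narrower term. Section 5 plans about 60 sites, so each will see few events. A suspicion may form only where events from all sites come together, which is with the Sponsor or the CI, and the text gives neither a way to act on it through SUSAR classification.

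The matter is sharpest for the resveratrol sub-trial. It is double-blind, and Section 9.2 says the product has no marketing authorisation anywhere, so a central view of serious events has particular value there.

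**Working it through.** No arithmetic applies, and the plan gives no figure to reproduce. The check sets the rules side by side and runs four kinds of unexpected SAE through them.

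**The rules**

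| Term or rule | Causality test | Who decides |
|---|---|---|
| AR (10.1) | Link cannot be excluded | Reporter or Sponsor |
| SAR (10.1) | Reasonable probability | Reporting investigator |
| SUSAR (10.1) | As for SAR, plus unexpected | As for SAR |
| SUSAR rule (10.2) | Related, no threshold given | Investigator or delegate |
| Central assessment (10.3) | No threshold given | CI, delegate or independent reviewer, only where local assessment is lacking |

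**The cases (each SAE is unexpected)**

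1. *The site judges the event related and reasonably probable.* It is an AR, a SAR and a SUSAR, and Section 10.2 expedites it. There is no conflict.
2. *The site gives no assessment.* Section 10.3 passes causality to the CI, a delegate or an independent reviewer. The case is covered.
3. *The site thinks a link possible but not probable.* The event is an AR. It fails the SAR row, and so the SUSAR row if SAR is read as defined. Section 10.2 asks only whether the investigator calls it related. An investigator using the AR test would say yes and the event would be expedited; one using the SAR test would say no. The outcome depends on which row is applied.
4. *The site says unrelated and the Sponsor suspects a link.* The event is an AR, because the Sponsor's judgement suffices. It is not a SAR, because the investigator does not hold the required belief. It is not a SUSAR under Section 10.2, because no investigator or delegate assigned it as related. The CI's causality role in Section 10.3 is not triggered, because a local assessment exists. The result is the same where the CI is the one who suspects; the AR row then applies if the CI is acting for the Sponsor, who delegates conduct of the trial to the CI (Section V).

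**Whether anything else brings case 4 back**

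- The CI's review of SUSARs starts only after an event has been classified as one.
- The CI's review of specific SAEs and SARs carries no stated power to reclassify.
- The Sponsor's verification and forwarding duties include no causality judgement.
- DMC review is periodic, anticipated every 12 months (Section VI). It cannot stand in for the 7-day and 15-day SUSAR limits in Section 10.2.

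Case 4 therefore has no stated route to expedited reporting. Case 3 has contradictory instructions.

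**The case against.** The strongest reply is that these events are not lost. Under Section 10.2 every non-exempt SAE, whatever its causality, goes to the Sponsor and the trials unit within 24 hours. The Sponsor reviews and tracks it to resolution, and line listings are reviewed monthly. Section 10.3 gives the CI continuing oversight of risk and benefit. It also has the DMC examine unblinded data for patterns that single cases would not reveal. All of this stands and limits the point: what is missing is the step from central suspicion to SUSAR status, not central sight of the events. Section 10.2 also refers to a Sponsor SOP that is not available here. It may contain such a step, but it would not remove the contradiction in the protocol that sites follow.

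Three stronger readings are tempting, and the text does not support them.

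- A reader might infer that the low threshold is kept for non-serious events and the high one for serious events. The AR row has no seriousness limit. A serious event can be an AR and still not a SAR, and that is the inconsistency. The SUSAR row could even be read as meaning an AR that is serious, so the table holds two competing readings and not one settled stricter rule.
- A reader might infer that no possible-but-not-probable event would be expedited. Section 10.2 asks only for relatedness and sets no threshold, so such an event is expedited if the investigator marks it related.
- A reader might take intracranial bleeding on aspirin or lactic acidosis on metformin as examples. The protocol treats both as recognised risks. If they are listed in section 4.8 of the product summaries, which are not shown, they may be expected and so not SUSARs whatever the causality wording.

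**Conclusion.** The point holds as an internal inconsistency with one practical consequence. Sections 10.1 and 10.2 give the Sponsor a voice in deciding what is an adverse reaction, then remove it for SARs and SUSARs. An unexpected SAE called unrelated on site but suspected by the Sponsor or CI has no stated path to expedited MHRA and REC reporting, and it would be missing from SAR and SUSAR counts. For events judged possible but not probable, the finding is weaker: the definitions conflict, and the operating rule does not settle which applies.

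The size cannot be given. The protocol states no SAE rate and no expected rate of disagreement between site and Sponsor. The planned 1339 participants and 97 months describe the whole trial, not the events affected. Those are the subset that are serious, unexpected, called unrelated on site and suspected centrally. The clearest case is an unexpected serious event on resveratrol.

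The conclusion assumes that the protocol text governs classification and that no unseen SOP supplies the missing step. It is worth correcting before further events accrue, but it does not show that safety oversight as a whole is inadequate.

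**What to change.** Three wording changes are enough.

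- **Section 10.1:** define a SAR as an adverse reaction, under the same causality test and with the same assessors, that is also serious. The SUSAR row then inherits the right test without further change.
- **Section 10.2:** in the SUSAR rule, let relatedness be assessed by the investigator or delegate, or by the Sponsor or CI. Add the same wording to the SAE form guidance.
- **Section 10.3:** reconcile the CI and Sponsor duties with this, so that the Sponsor's existing review of SAEs can raise causality and is not confined to cases without a local assessment.

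A clause forbidding the downgrading of an investigator's positive judgement is not needed to cure this defect, because nothing in the protocol permits such downgrading. A mandatory second causality review of every SAE also goes further than the defect requires.

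The cost is an amendment to the text and form guidance, and probably a few more expedited reports. No new data flow is needed, since the Sponsor already receives, reviews and tracks these SAEs.

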# 10.1.1 Adverse Events (AE)

#### Main trial

Adverse events will be collected from first dose up to visit 10 (week 156). All bleeding and GI adverse event grades (Common Terminology Criteria for Adverse Events, CTCAE v5), including grades 1-2, will be recorded on the AE eCRF. Any AE classified as related to the study IMP or procedures will be recorded and followed up on. For all other types of events only grade 3 and above will be collected and recorded in the AE eCRF.

Participants that experience any of the following should permanently discontinue aspirin immediately:

- aspirin-related severe toxicity (defined as ≥grade 3 CTCAE v5)
- significant gastrointestinal bleeding (grade 3 and 4)
- active gastrointestinal ulceration
- new cases or worsening tinnitus (grade 2 or above)
- intracranial bleeding
- hypersensitivity to aspirin.

IRAS: 1005142 Page **72** of **109** 

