#### 3.2 Secondary objectives

- 1) To assess the safety and tolerability of aspirin and metformin in combination compared to aspirin alone in the main trial.
- 2) To assess the safety and tolerability of each dose of resveratrol compared to placebo in the sub-trial.

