#### 7.3 Randomisation

**For the main trial**, participants will be randomised in a 1:1 ratio to aspirin or aspirin + metformin, with minimisation by BCSP centre. The main trial is open-label, so the research team and participants will be aware of their treatment assignment. However, we will minimise potential bias at the surveillance colonoscopy, by asking participants and the research team not to reveal their treatment assignment to endoscopy staff.

**For the resveratrol sub-trial**, two doses of resveratrol (5mg and 1g) are compared against a placebo control group. Participants will be randomised equally in a 1:1:1 ratio to the three treatment arms and according to aspirin or metformin use, ensuring an even distribution across arms of these factors. The sub-trial will be double-blinded, so the research team and participants will not be aware of treatment assignment.

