# Visit 5 (Week 52) – Research visit

The following procedures will be performed:

- Adverse events
- Concomitant medication recording
- Fasting blood samples & processing safety and research
  - Locally processed: Lipid profile, FBC, LFT, U&E, eGFR, HbA1c, glucose; vitamin B12 test for metformin arm participants only.
  - Research samples processed centrally: IGFBP-3, IGF-I, insulin, PK/PD, exploratory research biomarkers
- Faecal sample (using a FIT kit)
- Food Frequency Questionnaire
- Compliance (pill counting)
- Trial drug dispensed

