## Sub-trial

All Adverse Events will be collected from first dose up to visit 6 (54 weeks), and recorded in the AE section of the eCRF.

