## 11.3.3 Secondary outcome analysis

All secondary end-points will be analysed using the ITT population, with the exception of adverse events, for which we will analyse the safety population, consisting of all participants who received at least one dose of trial medication. Data on adverse events will be tabulated by randomised group. Logistic regression will be used to estimate odds ratios between randomised groups for polyp detection rate, polyp subtype and location. The relative recurrence of 'advanced' polyp detected at the first BCSP surveillance colonoscopy will be analysed using log-binomial regression model with robust standard errors to estimate the log relative risk. The region of the colorectum where polyps are detected at the first BCSP surveillance colonoscopy will be explored, possibly using a negative binomial random effects model with bivariate response (corresponding to polyp counts in the left and right colon) in which treatment and a baseline polyp count will be independent variables together with the random intercepts corresponding to patient and BCSP centre.

IRAS: 1005142 Page **79** of **109** 

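### Main trial: low-grade events outside bleeding and GI reach the eCRF only through an unblinded causality judgement, and B12 is tested in one arm only, so this part of the safety table is not comparable between arms

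*Protocol*

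**What the plan says.** Protocol section 10.1.1 gives three routes into the main-trial adverse event record:

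- Bleeding and gastrointestinal events of every grade, "including grades 1-2, will be recorded on the AE eCRF".
- A causality route: "Any AE classified as related to the study IMP or procedures will be recorded and followed up on".
- A grade threshold for the remainder: "For all other types of events only grade 3 and above will be collected and recorded in the AE eCRF".

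For the blinded resveratrol sub-trial the same section has no filter: "All Adverse Events will be collected from first dose up to visit 6 (54 weeks), and recorded in the AE section of the eCRF".

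Section 10.3 gives the causality judgement to the site principal investigator or a delegate. Section 7.3 states that "The main trial is open-label, so the research team and participants will be aware of their treatment assignment". The main-trial blinding described in section 7.4 covers endoscopy and laboratory staff, not those who assess adverse events.

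Section 2.5 requires yearly vitamin B12 tests in the aspirin plus metformin arm alone, citing a regulator's safety update. The visit schedule in section 7.7 repeats this at week 52 ("vitamin B12 test for metformin arm participants only"), at visit 7 and at week 154. B12 is not among the visit 1 bloods.

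The secondary objective in section 3.2 is comparative: "To assess the safety and tolerability of aspirin and metformin in combination compared to aspirin alone in the main trial". Section 11.3.3 gives the analysis: "Data on adverse events will be tabulated by randomised group".

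**The concern.** Limiting collection by event type or grade need not depend on the arm. Limiting it by relatedness, judged by someone who knows the arm, does. In the control arm the investigator asks whether aspirin could have caused the event; in the combination arm, whether aspirin or metformin could have. The same mild event can be recorded in one arm and left out in the other.

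One-arm B12 testing adds a second asymmetry: scheduled tests can find a low value in the combination arm only, and if a site calls it a related event, the causality route admits it at any grade.

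At stake is part of the secondary safety objective, and of the harms element in the first primary objective (section 3.1). A difference in these rows could come from the recording rule rather than the treatment. The analysis cannot correct this, because the missing events were never entered. Section 12.2 sends adverse events to the hospital notes as well, but the protocol plans no extraction from there for this comparison.

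**Working it through.** The plan states no figure on this point, so the check is a reading of the rules followed by an illustration.

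**Step 1. Which events depend on the causality judgement?**

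| Event type (main trial) | Recorded if judged unrelated? | Depends on causality? |
|---|---|---|
| Bleeding, any grade | Yes (10.1.1) | No |
| Gastrointestinal, any grade | Yes (10.1.1) | No |
| Any other, grade 3 and above | Yes (10.1.1) | No |
| Serious adverse event | Yes, apart from the exemptions in 10.1.2 (10.2) | No |
| Any other, grade 1-2 | No | Yes |

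Only the last row is exposed.

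**Step 2. Is that row empty in practice?** No. Section 8.8 names taste disturbance, separately from gastrointestinal disorders, as a common metformin effect, with frequency between 1/100 and 1/10. It is not among the most common aspirin effects listed there. If that frequency carried over to the 431 participants planned per arm (section 11.1), the combination arm would have between 431 × 0.01 = 4 and 431 × 0.10 = 43 cases. Background cases in the aspirin arm would be recorded only if someone attributed them to aspirin or to a trial procedure.

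**Step 3. How far could the recording rule move a row?** Let the true risk of a grade 1-2 event in this stratum be p in both arms, and let qA and qC be the probabilities that it is called related in the aspirin and combination arms. Then:

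- recorded count = 431 × p × q
- recorded risk ratio = (p × qC) / (p × qA) = qC / qA

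The true risk cancels, so the apparent ratio reflects attribution alone. All values of p and q below are assumptions; the protocol gives none.

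| qA vs qC | Recorded, p = 20% | Recorded, p = 40% | Recorded risk ratio |
|---|---|---|---|
| 20% vs 20% | 17 vs 17 | 34 vs 34 | 1.00 |
| 20% vs 30% | 17 vs 26 | 34 vs 52 | 1.50 |
| 20% vs 40% | 17 vs 34 | 34 vs 69 | 2.00 |
| 30% vs 20% | 26 vs 17 | 52 vs 34 | 0.67 |
| No filter (100% vs 100%) | 86 vs 86 | 172 vs 172 | 1.00 |

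For example, 431 × 0.20 × 0.30 = 26, and 0.30 / 0.20 = 1.50.

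**Step 4. B12.** Scheduled testing takes place in one arm at three visits and in the other arm at none. The protocol does not say whether a low result counts as an adverse event. It reaches the table only where a site records it, or something found through it, as one.

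**The case against.** The strongest reply is about scope. The safety outcome in section 3.5 singles out bleeding and gastrointestinal tolerability, which are exactly the categories collected at all grades in both arms. Most of the common reactions listed in section 8.8 fall there too. A reader might infer that the whole safety comparison is biased; the documents do not support that, and this part of the objection stands.

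A second reply concerns direction. A reader might infer that the distortion must always count against the combination. Aspirin is in both arms, and section 10.1 sets a low bar for relatedness in both: it need only be impossible to exclude. Reversed attribution reverses the sign, as the 0.67 row shows. Two candidate drugs and one-arm testing make the direction likely, not certain. This stands as well.

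On B12, a reader might infer that the aspirin arm can show no deficiency at all. That goes too far: a clinically diagnosed deficiency or consequence of grade 3 or above would be recorded in either arm, and full blood counts are taken in both arms at the same visits. The one-arm test is also openly stated as safety monitoring. Nor does the protocol list fatigue or weight loss as metformin reactions, so they cannot serve as examples.

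The contrast with the sub-trial does not prove an error. Resveratrol has no marketing authorisation (section 9.2), which is reason enough to collect everything there; aspirin and metformin are licensed drugs (section 8.2).

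Finally, table layout commonly belongs in the SAP, and section 11.3.3 names no safety test. That is fair as to layout. It does not reach the collection rule, which the protocol fixes and no SAP can undo.

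**Conclusion.** The point holds for one stratum. In the main trial, recording of grade 1-2 events outside bleeding and gastrointestinal disorders depends on an unblinded causality judgement, and protocol B12 testing is confined to one arm. Tabulating these findings by randomised group risks differential ascertainment, probably against the combination.

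The size cannot be derived from the documents. The ratios of 0.67 to 2.00 rest on assumed attribution rates and show only that the recorded ratio equals the attribution ratio whatever the true risk. If attribution were equal in the two arms, there would be no distortion from the filter. The B12 element further assumes that sites record low results as adverse events.

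The comparison of bleeding, gastrointestinal, grade 3 and above, and serious events is not affected by the filter. This is a cheap improvement to how a secondary objective is answered and does not undermine the trial's safety assessment as a whole.

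**What to change.** In sections 10.1.1 and 11.3.3, state that the between-arm safety comparison uses only the categories collected regardless of causality: bleeding at all grades, gastrointestinal events at all grades, all events of grade 3 and above, and serious adverse events. Report related grade 1-2 events of other types, and any adverse events arising from protocol B12 testing, descriptively within each arm, labelled as not comparable between arms. B12 safety monitoring itself stays as it is.

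The cost is wording in two sections, with no new visits, samples or assays. The downside is that the comparative table holds fewer event types; for example, low-grade taste disturbance would be described within arm and not compared.
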